10. WITHDRAWAL OF SUBJECTS

Subjects must be withdrawn under the following circumstances:

- 10.1. The subject withdraws consent
- 10.2. Discretion of investigator/study staff

10.3. There is set criteria that will be used to determine if the subject qualifies to participate in this study. Based on the discretion of the investigator/study staff and/or the evaluation of the qualifying criteria they may be excluded from this study.

- If the investigator/study staff notices a trend with (not limited to these examples) the subjects' blood pressure fluctuating outside the parameters, their heart rate fluctuating outside the parameters, their need to repetitively void early and/or their inability to remain still for the majority of the study they will be removed from the study and may not be used as a participant in that particular study in the future.

11. ADVERSE EVENTS

Definitions ([REDACTED]):

Adverse event: Any untoward medical occurrence in a subjects, users or other persons, whether or not related to the medical device under study.

Device-related adverse event: Adverse event related to, associated with, or caused by, the use of a medical device under study, including but not limited to events that may have been attributed to the device because of device failure or malfunction, improper or inadequate design, manufacture or user error.

Device deficiency: Inadequacy of a medical device with respect to its identity, quality, durability, reliability, safety or performance. Device deficiencies include malfunctions, use errors and inadequate labeling.

- Device deficiencies will be reported according to department procedures.

Serious adverse event: Adverse event that: a) led to death, b) led to serious deterioration in the health of the subject, that resulted in: (i) a life-threatening illness or injury, (ii) a persistent or significant impairment of a body structure or a body function, (iii) in-patient or prolonged hospitalization, or (iv) medical or surgical intervention to prevent life-threatening illness or injury or permanent impairment to a body structure or a body function, or c) led to fetal distress, fetal death or a congenital abnormality or birth defect. NOTE: Planned hospitalization for a pre-existing condition, or a procedure required by the clinical investigational plan, without serious deterioration in health, is not considered a serious adverse event.

All adverse events, including inter-current illnesses will be reported and documented as described below.

11.1. Adverse Events

- 11.1.1 All adverse events that occur during the study shall be recorded on the Case Report Form even if the investigator/study staff assesses the adverse event as unlikely to be causally related to the test device or study procedures.

11.2. Serious Adverse Events

- 11.2.1 The investigator/study staff shall promptly report both serious adverse events and unanticipated adverse device effects to the sponsor within 48 hours. All serious adverse events will also be reported to the IRB per IRB reporting requirements.
- 11.2.2 At the time of discharge from the study, any unresolved serious adverse event(s) will be followed up by the investigator/study staff until the event(s) are resolved, stabilized or the patient is lost to follow-up or the adverse event is otherwise explained. The investigator/study staff will also instruct the subject to report any subsequent events occurring in the next 30 days, which the subject or the subject's physician believes might reasonably be regarded as caused by or have a reasonable possibility of being caused by the test device or procedures involved in the study.

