6.6.1 The total time will be approximately

6.6.2 At the conclusion of the procedure, the sensors/devices [REDACTED] and the arterial line(s) will be removed and the volunteer will be allowed to leave after medical personnel determine it is safe to do so.

6.6.3 All volunteers will be encouraged to remain in the study area until they feel fit to leave; subjects should feel safe and able before returning to work directly after participation in the study. All subjects including subjects that are employees of Masimo will be advised to take as much time as they need after the study before returning to work.

6.6.4 Volunteers will be given instructions on wound care. All volunteers will be instructed to contact the principal investigator and/or study staff in the event of any potential complication.

6.6.5 Volunteers will be paid according to the compensation breakdown on the consent form.

6.6.6 Subjects will be provided with information related to any significant new findings that develop at any time during the study which may relate to their willingness to continue their participation, their health and/or medical care.

6.7**TIMING REQUIREMENTS FOR SUBJECT PARTICIPATION**

[REDACTED]	[REDACTED]

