13.1.2. Device Risk

13.1.2.1. The noninvasive devices used in this study are similar in technology and design to some commercially available pulse oximeters and other non-invasive devices and hence have the same risks. Pulse oximeters and other non-invasive devices are commonly used and are considered to be minimal risk.

13.1.2.2. There is an extremely small risk of damage to the subject's fingers, or other locations where sensors are placed, from the device including temporary skin irritation or discomfort associated with exposure to the sensor as well as potential temporary mechanical irritation or discomfort. There is a remote, yet possible, risk of a burn from the sensor. In the case of a sensor burn there is the potential for permanent skin damage (scar/discoloration).

13.1.2.2.1. If there are any cuts and/or abrasions near the finger nail certain types of sensors may not be placed on the particular finger to avoid any discomfort for the subject.

13.1.4. Arterial Cannulation Risks:

13.1.4.1. The radial artery is the most common site for invasive blood pressure monitoring in anesthesia and critical care medicine because it is technically easy to cannulate and complications are uncommon, in part owing to the good collateral circulation of the hand. The widespread application of invasive

arterial pressure monitoring in anesthesia and intensive care is related to the extremely good safety record of this technique.

13.1.4.2. Other risks include bleeding, infection, hematoma, damage to the blood vessel and surrounding nerves, tendons or tissue; loss of feeling in hand and/or arm and even the loss of hand due to rare complications of the study.

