13.1.8. Ethyl Chloride (Lidocaine Spray)

13.1.8.1. Ethyl Chloride is a topical anesthetic which is used to prevent pain by cooling the skin.

13.1.8.2. Although unlikely, the anticipated adverse events that may occur, include but are not limited to:

- 13.1.8.2.1. Changes in skin color (ie. Flushing or redness of the skin)
- 13.1.8.2.2. Delayed wound healing
- 13.1.8.2.3. Rash
- 13.1.8.2.4. Itching
- 13.1.8.2.5. Swelling

These adverse events are expected to be temporary.

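### Staff follow-up after discharge is limited to serious events, so a nerve injury or sensor burn that looks minor on the day is left to the subject to report

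*Protocol*

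**What the plan says.** **Follow-up by staff.** Protocol 11.2.2 says that, at discharge, "any unresolved serious adverse event(s) will be followed up by the investigator/study staff until the event(s) are resolved, stabilized". It adds two further end-points: loss to follow-up, and some other explanation of the event. The duty is confined to serious events.

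**Recording.** 11.1.1 says "All adverse events that occur during the study shall be recorded on the Case Report Form", whatever the presumed cause. It sets no follow-up to an outcome.

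**Seriousness.** Among the outcomes that make an event serious, section 11 lists "a persistent or significant impairment of a body structure or a body function". It also lists intervention to prevent permanent impairment.

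**Discharge.** Under 6.6.2 the volunteer may leave once sensors and lines are out and medical personnel judge it safe.

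**Routes that depend on the subject.** There are two.
- 6.6.4: "Volunteers will be given instructions on wound care", and "All volunteers will be instructed to contact the principal investigator and/or study staff in the event of any potential complication".
- 11.2.2: staff will "instruct the subject to report any subsequent events occurring in the next 30 days", if the subject or the subject's physician thinks the device or procedures may reasonably have caused them.

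**Named harms.** 13.1.4.2 lists, for the arterial line, "damage to the blood vessel and surrounding nerves, tendons or tissue; loss of feeling in hand and/or arm". 13.1.5.2 gives a similar list for blood draws. 13.1.2.2 accepts a remote risk of a sensor burn that could leave a permanent mark.

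**The concern.** The follow-up rule depends on a classification that, for some injuries, needs follow-up to settle. Numbness in a finger may clear within hours or may last. While the volunteer is still in the room, staff cannot know which. If it is classed as non-serious at that moment, 11.2.2 asks nothing more of staff, although further contact is what would show whether the impairment persists.

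Two things are at stake. The first is the subject: these are healthy volunteers, some of them sponsor employees whom 12.4.1 calls vulnerable, and section 15 offers them no personal benefit. The second is the safety record. An event can stay on the Case Report Form with no outcome. A change from non-serious to serious can go unseen, and then neither the 48-hour report to the sponsor nor the report to the IRB in 11.2.1 is made.

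**Working it through.** No arithmetic applies: the plan gives no event rates, and its sample size section is redacted. The check is to sort events by their state at discharge and ask what the visible text requires for each.

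| State at discharge | Duty on staff afterwards | Route open to the subject |
|---|---|---|
| Resolved | None needed | 6.6.4 or the 30-day clause if it recurs |
| Unresolved, serious | Follow to an end-point (11.2.2) | Same |
| Unresolved, not serious | None stated | 6.6.4; the 30-day clause only if it counts as a subsequent event |
| Not yet present | None stated until reported | 6.6.4; the 30-day clause |

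The third row is the gap. Four questions decide how wide it is.

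1. **Can a named injury fall in that row?** Yes. The impairment criterion is met by persistence or by significance. Loss of feeling that is clearly significant on the day, or a burn that needs intervention to prevent permanent impairment, is serious at discharge and belongs in row two. A milder numbness or a small burn meets neither test on the day. It could become serious later only by persisting (or worsening), and that lies in the future.

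2. **Do the subject's own routes cover it?** In part. 6.6.4 is broad: it has no time limit, no seriousness test and no causality test. It still relies on the subject to call. The 30-day clause also relies on the subject. It adds a causality judgement and is worded for subsequent events, a term the protocol does not define. Whether an injury already open at discharge qualifies is unclear. Neither route states what staff do once a report arrives.

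3. **Would 11.2.1 catch a later change?** Only if staff learn of it. The section has no cut-off at discharge, so a serious event reported by telephone falls within it. It does not say when the 48 hours begin. It also covers unanticipated adverse device effects, but harms that section 13 lists in advance are hard to call unanticipated.

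4. **Would a later report be recorded?** This is not clear. 5.4.5 says generally that adverse events are recorded. The operative rule in 11.1.1 covers events during the study, and the text does not say whether the 30 days count as part of it.

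The protocol itself treats the wrist as at risk beyond the visit: section 9 excludes people who plan to strain it within 24 hours after an arterial procedure.

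**The case against.** The strongest reply is that the plan does not abandon these subjects. Medical personnel clear each volunteer to leave, every volunteer gets wound care advice, and every volunteer is told to call about any possible complication. The devices are non-significant-risk and the subjects healthy. Much of this stands, and it rules out several stronger readings that a reader might infer.

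- **That the injuries are wholly unfollowed.** The documents do not support this. They are not followed by staff, but 6.6.4 gives an unfiltered way to report, and the 30-day clause admits the view of the subject's physician as well as the subject's own.
- **That the 11.2.1 reports cannot be triggered after discharge.** They can. They fail only if the subject stays silent.
- **That every such injury counts as non-serious at discharge.** Some would already be serious, as significant impairment or through the need for intervention.
- **That the plan's statements about temporary effects become untestable throughout.** The lists in 13.1.5.3 and 13.1.9.3 are of symptoms such as faintness, nausea and sweating, not the injuries at issue. Only 13.1.8.2 joins that expectation to a relevant harm, "Delayed wound healing", which it calls unlikely.
- **That staff should follow every open event.** 13.1.5.1 puts hematoma and bruising among the commonest complications of blood draws. Following each bruise to resolution would cost much more and add little.

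It is also fair to say that the Post Care Instructions, consent form and Case Report Form are not among the documents supplied, and that parts of section 6, including its timing table, are redacted. A follow-up contact could be described there. 11.2.2 itself is fully visible.

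What the reply does not meet is the point in row three: the duty on staff ends at discharge for an injury whose seriousness cannot yet be known.

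**Conclusion.** The concern holds in a limited form. For nerve or tendon damage, loss of feeling or a sensor burn that is unresolved but looks non-serious at discharge, the visible text requires no staff follow-up and relies on the subject to report. If the subject does not, a change to serious may not reach staff and the 11.2.1 reports may not be made.

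The size cannot be put as a count, since no rates are given. The protocol describes these harms as rare or remote, so few subjects are likely to be affected. The analysis of device accuracy is untouched. This is a cheap improvement to subject safety and the safety record, not a flaw that undermines the study.

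The conclusion rests on two assumptions: that no unseen document already requires such contact, and that discharge in 11.2.2 means the volunteer's departure under 6.6.2.

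**What to change.** In 11.2.2, extend staff follow-up to any adverse event unresolved at discharge that could become a persistent impairment. Name at least nerve or tendon injury, loss of feeling and sensor burn. Uncomplicated bruising can stay with self-report. Keep the existing end-points, re-assess seriousness at each contact, and start the 11.2.1 clock when staff learn that an event has become serious.

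In 11.1.1, state that events reported after discharge, including those in the 30-day window, are entered on the Case Report Form.

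The cost is a short amendment needing IRB approval (18.1) and a few extra contacts by existing staff, only for subjects who leave with such an event. If the Post Care Instructions already provide for this contact, a cross-reference in 11.2.2 would cover the contact itself; the points on seriousness, the 11.2.1 clock and recording would still need stating if they are not there.

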12. MEASURES TAKEN TO PROTECT THE RIGHTS AND WELFARE OF SUBJECTS

- 12.1. All subjects will be monitored closely throughout the study. There will be an ACLS certified medical doctor present in the study area throughout the study.
- 12.2. The following measures will be taken to insure the confidentiality of the subjects:
 - 12.2.1. A code (identification) number for each subject will be kept on file.
 - 12.2.2. Only their corresponding identification number will identify subjects.
 - 12.2.3. Access to identifying documents (IC, SSN, Photo ID) and data will only be made to the principal investigators in the study and study staff.
 - 12.2.4. The confidentiality and retention of these documents will be protected to the extent provided and required by the law.
- 12.3. Documents and Database

12.3.1. Documents will be kept a minimum of 5 years after the specific product/tested for is no longer being made. If destroyed, these documents will be shredded and done by a certified company used for destroying medical and clinical data

12.4. Vulnerable Populations

12.4.1. Employees are considered to be a vulnerable population

12.4.1.1. Participation is not a condition of employment. There will be no repercussions in the workplace in the case that the employee refuses to participate in the study or withdraws at any point during the study.

12.4.1.2. Neither supervisors nor superiors will be involved in the recruitment of employees for participation in the study.

12.4.2. Economically disadvantaged or unemployed and educationally disadvantaged

12.4.2.1. Reasonable compensation will be provided for economically disadvantaged subjects to eliminate possibility of undue influence due to financial incentive.

12.4.2.2. Educationally disadvantaged subjects will be provided ample time to ask questions and comprehend information

13. RISKS/DISCOMFORTS

The studies will be conducted per IRB approved procedures. The study subjects will consist entirely of healthy volunteers. The readings obtained during the study will be recorded but will not be used in patient care, monitoring, or diagnosis.

13.1. Risks

13.1.1. Risks can be categorized into the following categories:

- Those associated with the device
- Those associated with placement of the arterial line (arterial cannulation)
- Those associated with blood draws
- Those associated with inflicted knowledge
- Those associated with the Lidocaine injection
- Those associated with the Lidocaine spray
- Those associated with low oxygen concentration
- Those associated with oxygen administration
- Those associated with the nose clip
- Those associated with loss of confidentiality/privacy
- Those associated with Additional testing

Note: In the very unlikely, worst case, complications from the study may result in death. The study shall be stopped by the subject or study staff long before this would occur.

13.1.2. Device Risk

13.1.2.1. The noninvasive devices used in this study are similar in technology and design to some commercially available pulse oximeters and other non-invasive devices and hence have the same risks. Pulse oximeters and other non-invasive devices are commonly used and are considered to be minimal risk.

13.1.2.2. There is an extremely small risk of damage to the subject's fingers, or other locations where sensors are placed, from the device including temporary skin irritation or discomfort associated with exposure to the sensor as well as potential temporary mechanical irritation or discomfort. There is a remote, yet possible, risk of a burn from the sensor. In the case of a sensor burn there is the potential for permanent skin damage (scar/discoloration).

13.1.2.2.1. If there are any cuts and/or abrasions near the finger nail certain types of sensors may not be placed on the particular finger to avoid any discomfort for the subject.

13.1.4. Arterial Cannulation Risks:

13.1.4.1. The radial artery is the most common site for invasive blood pressure monitoring in anesthesia and critical care medicine because it is technically easy to cannulate and complications are uncommon, in part owing to the good collateral circulation of the hand. The widespread application of invasive

arterial pressure monitoring in anesthesia and intensive care is related to the extremely good safety record of this technique.

13.1.4.2. Other risks include bleeding, infection, hematoma, damage to the blood vessel and surrounding nerves, tendons or tissue; loss of feeling in hand and/or arm and even the loss of hand due to rare complications of the study.

13.1.5. Blood Draw Risks

13.1.5.1. Discomfort is generally associated with needle puncture. The most common complications associated with blood draws are hematomas or bruising.

13.1.5.2. There is also a possible risk of infection, tendon or tissue damage, damage to the blood vessel and surrounding nerves, loss of feeling in hand and/or arm and even the loss of hand due to rare complications of the study.

13.1.5.3. Other anticipated adverse events that may occur, include but are not limited to:

- Vasovagal (fainting)
- Lightheadedness
- Feeling flush/ warm
- Feeling nauseated
- Throwing up
- Seizures
- Sudden drop in blood pressure/ sudden increase in blood pressure
- Sudden drop in heart rate/ sudden increase in heart rate
- Tingling sensation of face, arms and/or legs
- Sweating
- Mouth dryness

These anticipated adverse events are expected to be temporary.

The listed discomforts and complications associated with blood draws can be expected and are not an act of neglect, failure to follow standards or related to the sensors or devices used in the study.

13.1.6. Risk from Inflicted Knowledge

13.1.6.1. The risk of inflicted medical knowledge to volunteers is negligible since we de-identify all associated sample information including those relevant to our clinical and engineering parameter studies. The monitoring and test results are not examined for diagnostic purposes and do not reflect an attempt to ascertain any subject's medical condition. The attending physician's role during this study is to ensure the safety of the subject during the study. We will reduce the risk of inflicted knowledge by assuring the subjects that device readings and blood measurements are for research use only. In the case that a subject becomes aware of a condition (anemia, hypertension, arrhythmia etc.) they have during the course of our study our study staff will recommend that they contact their primary care physician and we will document this recommendation. As part of that process we will follow up with these individuals prior to enrollment if their condition meets exclusion for that particular study.

13.1.7. Lidocaine (injection) risks

13.1.7.1. Insertion of the Lidocaine may be discomforting and can feel like a slight pinch along with a warm/burning sensation.

13.1.7.2. Other anticipated adverse events that may occur, include but are not limited to:

- Flushing or redness of the skin
- Itching skin
- Small red or purple spots on the skin
- Unusually warm skin
- Bruising
- Bleeding at the application site
- Swelling

These adverse events are expected to be temporary.

Although not common, it is also possible to have an allergic reaction to injectable lidocaine. Subjects should not take part in this study if they are allergic to lidocaine injection or other types of numbing medicine, or if they have a heart rhythm disorder called Wolff-Parkinson-White Syndrome or Stokes-Adams syndrome. Subjects are instructed to tell the study staff right away if they experience hives; difficulty breathing; swelling of your face, lips, tongue or throat.

13.1.8. Ethyl Chloride (Lidocaine Spray)

13.1.8.1. Ethyl Chloride is a topical anesthetic which is used to prevent pain by cooling the skin.

13.1.8.2. Although unlikely, the anticipated adverse events that may occur, include but are not limited to:

- 13.1.8.2.1. Changes in skin color (ie. Flushing or redness of the skin)
- 13.1.8.2.2. Delayed wound healing
- 13.1.8.2.3. Rash
- 13.1.8.2.4. Itching
- 13.1.8.2.5. Swelling

These adverse events are expected to be temporary.

13.1.9. Low Oxygen Concentration

13.1.9.1. Risks associated with hypoxia include dizziness, shortness of breath, drowsiness, or headache. If or when this occurs, the study can be stopped.

13.1.9.2. There is an extremely small risk of loss of consciousness or death from lack of oxygen. The study shall be stopped by the subject or clinical staff long before this could occur.

13.1.9.3. Other anticipated adverse events that may occur, include but are not limited to:

- Vaso vagal (passing out)
- Lightheadedness
- Feeling nauseated
- Throwing up
- Seizures
- Sudden drop in blood pressure/ sudden increase in blood pressure
- Sudden drop in heart rate/ sudden increase in heart rate
- Tingling sensation of face, arms and/or legs
- Sweating
- Mouth dryness

13.1.9.3.1. These anticipated adverse events are expected to be temporary.

